1. BACKGROUND AND SIGNIFICANCE

An increasing number of people is interested in consuming either grass-fed beef or plant-based beef alternatives, such as the Impossible BurgerTM or Beyond MeatTM, believing that these choices are beneficial for consumer health; however, little to no work has been performed to study these beliefs and claims. The *purpose of this study* is to evaluate effects of plant-based meat, grass-fed beef, and grain-fed beef on postprandial plasma inflammatory and metabolite profiles in middle aged adults (30-60 y old). This work will offer new insight into manipulating the acute, post-meal inflammatory state by consumer food choices. It will also provide more insight how food-derived metabolites impact systemic metabolites in the human body through metabolomics analysis. This study will utilize a randomized cross-over design and every participant will consume each type of meat on three separate occasions separated by a minimum of three days.

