2. STUDY OBJECTIVES

- To determine the effects of consuming 9 oz of the Impossible BurgerTM, grass-fed beef or grain-fed beef on 300 min postprandial plasma inflammatory markers (IL-6, TNF-α, C-reactive protein, and VCAM-1).
- o To determine effects on plasma metabolites (vitamin and mineral derivatives, phenolics, amino acids etc.) collected through regular urine sampling during the 300 min postprandial phase (at 60 min, 180 min, and 300 min).
- o To determine the effects on subjective satiety at 30, 60, 90, and 120 min and every hour thereafter following consumption.

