3.3 Study Schedule

Participants will be asked to complete one screening/consent visit and three testing visits throughout their participation in the study. All visits will take place in clinical research space located at the Center for Human Nutrition Studies (CHNS). The research team will accommodate the availability of the research participants, including weekend days if needed. The table below describes these activities.

Visit	Timepoint	Activities	Location	Duration
Phone Screen	Week 1	- Pre-screening questions to	Virtual	15 min
		determine eligibility.		
Consent	Week 1	- Consent (online or in person)	Virtual or CHNS	1 hour
Screening	Week 1	Height/weightBlood drawScreening questionnaires	CHNS	1 hour
Metabolic visit (3 visits separated by	Week 2-4	IV PlacementEat study provided mealPostmeal phase (300 min)	CHNS	7 hours each
3-7 days)		- Regular urine and blood collection		

Version 1 Page 3 of 9

^{*} Participants that are pregnant or planning on becoming pregnant in the next month are excluded. The justification is the documented alterations in metabolism that occur during pregnancy (Lain and Catalano, 2007), which would impact our metabolomics analysis in this study.

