Metabolic visits (Weeks 2-4. Number of Visits: 3. Duration: 7 hours each): These three visits will take approximately 7-hours each and will take place at The Center for Human Nutrition Studies (CHNS). Visits will be at least 3 days apart. Participants are required to fast for 12 hours prior to reporting to the laboratory. During this, participants will complete the following:

- Meat consumption: Using a randomized cross-over design, participants will ingest 250 g (9 oz) of an Impossible BurgerTM burger (plant), a grain-fed beef burger (grain-fed), a grass-fed beef burger (grass-fed). The meat will be stored as 9 oz. (250 g) patties in designated food freezers (-40 °C) in the NDFS kitchen and thawed overnight in a refrigerator (4 °C) prior to the subject's arrival the next morning. The meat will be cooked on a griddle in the CHNS metabolic kitchen on each side until an instant-read meat thermometer registers an internal temperature of 160 °F (71 °C). The patties will then be immediately served to the participant. Participants are provided with a standardized amount of water (1.5 liters) to drink during the 300 min post-meal phase. Participants will be asked to eat and drink the water at a comfortable rate but to try and finish within 30 min. No other food is allowed to be consumed during the ensuing 300 min postprandial phase. No other liquids are allowed to be consumed during that time as this would interfere with our protocol (see urine collection below). Subjects are also expected to remain seated in a chair during this time and can work/read/or watch entertainment on their own electronic device. Participants will be allowed to get up and use the rest-room; however, we will ask participants to remain sedentary otherwise.
- o **Blood Draws:** An intravenous catheter (IV) will be temporarily placed into a forearm or hand vein by a trained member of the study team (the PI) to collect repeated blood samples. The catheter will remain viable by a slow drip of saline. We will collect four samples total (10 mL each; 40 mL or 2 ½ tablespoons) on each of the three metabolic visits. One sample will be collected right before participants eat and three more samples will be collected at 60, 180 min and 300 min after they consume the meal. These draws will be taken in a private room in clinical facilities, in a reclining leather chair. Participants will be provided with their

Version 1 Page 5 of 9

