7. ANALYTICAL PROCEDURES AND STATISTICAL CONSIDERATIONS

- o **Inflammation:** Inflammatory biomarkers (IL-6, VCAM-1, TNF-alpha and C-reactive protein [CRP]) will be measured using ELISA kits at Dr. [name]'s laboratory at Utah State University. Plasma samples will be stored at -80°C until cytokine analyses are performed.
- Metabolomics: Mass spectrometry techniques will be used for untargeted and/or targeted assessment of blood and/or urinary metabolites. This analysis will give insight into the appearance of food-derived metabolites in the human body and how they may impact inflammatory responses after eating. This analysis will be performed using de-identified samples by Metabolon Inc (a company dedicated to metabolomics analysis) and/or the Plant for Human Health Institute. Samples will be provided to these core services as de-identified samples. No other data will be shared with these core services. Plasma and urine samples will be stored at -80°C until metabolomics analyses are performed.

Version 1 Page 7 of 9

- o **Dietary logs:** The Diet History Questionnaire III (NIH) and 3-day food records will be analyzed by dietetic staff within Dr. [name]'s laboratory at Utah State University.
- Statistical analysis: Change scores (post-dietary intervention baseline) will be created for all inflammatory biomarkers and metabolites. Metabolic intermediate data will be reduced into Metabolic Factors using Principal Component Analysis (PCA) of the change scores. Factor scores will be computed for each individual for both diets. Change scores and factor (change) scores for both diets will be compared using paired t-tests. P< 0.05 will be considered statistically significant and analyses will be performed in SAS 9.4 (SAS, Cary, NC).

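### The analysis is written for two diets while the trial compares three burgers, and it names no contrasts, no post-meal value and no error rule beyond P<0.05

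*Combined protocol and SAP*

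**What the plan says.** In section 7, the statistical analysis paragraph forms change scores for the inflammatory markers and metabolites and reduces the metabolite changes by PCA. It continues: "Factor scores will be computed for each individual for both diets". The test is then given: "Change scores and factor (change) scores for both diets will be compared using paired t-tests". P<0.05 is the only significance rule.

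The design has three conditions. Section 1 says "every participant will consume each type of meat on three separate occasions separated by a minimum of three days", and section 3.3 provides "three testing visits throughout their participation in the study", so each participant eats one plant, one grain-fed and one grass-fed burger. On blood sampling, section 3.3 says "One sample will be collected right before participants eat and three more samples will be collected at 60, 180 min and 300 min" after the meal. Section 7 defines the change score only as post-intervention relative to baseline.

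Two other places touch on the gaps. Section 2 sets the inflammatory objective as the effect of the plant burger, "grass-fed beef or grain-fed beef on 300 min postprandial" plasma markers. The power calculation in section 7 assumes P ≤ 0.05 together with Q ≤ 0.3 for untargeted metabolomics.

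**The concern.** Two diets cannot be the whole comparison in a three-burger trial. The text does not say which two are meant, or how the third enters the PCA and the tests. It does not say which post-meal sample, or what summary of the three, makes the change score. Two analysts could both follow the paragraph faithfully and report different results.

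The trial's purpose is the comparison of all three burgers. If the contrasts and the time are chosen after the data are seen, the reported P-values cannot be interpreted. Even if they are chosen in advance, P<0.05 on every test leaves a sizeable chance of a false burger difference. For metabolites, it may also fall short of the false-discovery level on which the plan's own sample size rests.

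**Working it through.** **1. The plan's own figures.** The number recruited reproduces: 24/(1 − 0.20) = 30. The 89-93% true discovery rate attached to n=24 does not reproduce for the planned test. As 1 minus the false share at P ≤ 0.05 with 80-120 true differences, it comes to 72-83% (step 5). The nearest match is average power at Q = 0.3 from a two-independent-group normal formula, 87.1-91.6%, which is not a paired analysis. The present point does not depend on that figure.

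**2. Number of conditions.** Section 7 has two diets, stated twice. Sections 1, 2 and 3.3 have three burgers. Three burgers give three pairwise contrasts: plant v grain-fed, plant v grass-fed, grass-fed v grain-fed. None is named.

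**3. Post-meal value.** There are three post-meal samples, at 60, 180 and 300 min. The 300-min wording in section 2 could mean the last sample or the whole window. The same list describes metabolite sampling as "collected through regular urine sampling during the 300 min postprandial phase (at 60 min, 180 min, and 300 min"), which uses 300 min as a window. The objective therefore fixes no value for analysis.

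**4. False claims on the inflammatory markers.** Inputs: n=24 (section 7), four markers (section 7), two-sided 0.05 (sidedness assumed) and no diet effect. The method is simulation of three paired t-tests per marker on one value per visit.

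- One marker, three contrasts: 12-13%. If the contrasts were independent: 1 − 0.95³ = 14.3%.
- Four markers, three contrasts: 41%, 39%, 35-36% and 30% for assumed marker correlations of 0, 0.3, 0.5 and 0.7. If independent: 1 − 0.95¹² = 46.0%.
- Four markers, three contrasts, all three times tested: 63-75% (assumed between-time correlation 0.8 to 0.5, marker correlation 0.3 to 0).

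**5. False share among metabolites called different.** Inputs from the power calculation: 600 metabolites, mean difference 0.2624, SD 0.3, n=24. Assumed within-person correlation r is 0 or 0.5. The SD of the paired difference is 0.3·√(2(1 − r)), which is 0.424 or 0.300. Paired-t power at 0.05 is 0.827 or 0.984. With m true differences, for one contrast at one value per visit:

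false share = 0.05(600 − m) / [0.05(600 − m) + power × m]

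| m | r = 0 | r = 0.5 |
|---|---|---|
| 20 | 29/(29 + 16.5) = 0.637 | 29/(29 + 19.7) = 0.596 |
| 40 | 28/(28 + 33.1) = 0.458 | 28/(28 + 39.4) = 0.416 |
| 80 | 26/(26 + 66.2) = 0.282 | 26/(26 + 78.7) = 0.248 |
| 120 | 24/(24 + 99.2) = 0.195 | 24/(24 + 118.1) = 0.169 |

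P<0.05 alone therefore misses 0.3 for the 20-40 that the power paragraph calls conservative, and meets it for the 80-120 that the same paragraph attaches to n=24. Holding the share at 0.3 needs a P cut of 0.0083-0.0297 when m is 20-40. When m is 80-120, the cut would be 0.055-0.107.

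**The case against.** The strongest reply is that the two-diet wording means each pair in turn, that a paired t-test on change scores is a valid crossover analysis, and that this is a study seeking insight, with no marker named primary and a sample size based on metabolomics.

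Much of that stands. A reader might infer that paired t-tests are the error or that a mixed model is obligatory. The documents do not support this: the test is valid once the contrast, the value and the error rule are stated. Family-wise control across four markers is a choice, and naming a lead marker with the rest exploratory is equally defensible. The 30-41% assumes no burger differs on any marker, so it is not a forecast for this trial. Nor do the documents show that P<0.05 must breach Q ≤ 0.3 for metabolites, because with 80-120 true differences it does not.

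The pair-by-pair reading is nowhere stated, however, and it still leaves three unadjusted tests per marker at an unnamed time.

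A reader might also infer that Q ≤ 0.3 should simply govern everything in section 7. The power calculation gives it for untargeted metabolites, alongside P ≤ 0.05, and says nothing of PCA factors. On a few independent null factors, a Benjamini-Hochberg rule at 0.3 makes a false claim about 30% of the time. P<0.05 does so in 1 − 0.95³ = 14% for three factors, 23% for five and 26% for six (the number of factors is assumed). Q alone would also loosen the metabolite rule if 80-120 differ, since the cuts in step 5 then exceed 0.05.

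**Conclusion.** The analysis paragraph is wrong as written and should be corrected before outcome data are examined. The conflict between two diets and three burgers, and the missing contrasts and post-meal value, follow from the text alone and rest on no assumption.

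The sizes are conditional. The false-claim figures for the markers assume 24 completers, one value per visit, no diet effect and the stated marker correlations. The metabolite figures assume the power paragraph's inputs and a within-person correlation of 0 to 0.5, and whether the planned Q is met turns on which of that paragraph's two counts of true differences applies.

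The documents do not show that the investigators intend to drop a burger. They show that the written rule does not say what happens to the third. The conflict over how urine is collected and the absence of a satiety analysis are separate points.

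**What to change.** 1. Replace the two-diet wording with all three burgers, name the three pairwise contrasts, and run the PCA and factor scores on all three.
2. Fix in advance one change value per visit for each inflammatory marker: either the average change over the 300-min window or the change at 300 min.
3. Keep the paired t-tests and control error over the three contrasts within each marker. The simplest rule that does not need equal spread: the smallest of the three P-values must be ≤ alpha/3, after which the other two are judged at alpha. If spread is similar across burgers, an alternative is an overall three-burger test at alpha (participant random, diet and period fixed), followed by the paired t-tests at alpha.
4. Across the four markers, either use alpha = 0.05/4 = 0.0125 for each (so alpha/3 = 0.0042), or name one lead marker at 0.05 and label the others exploratory.
5. For metabolites, require both P ≤ 0.05 and Q ≤ 0.3, and state whether Q runs per contrast or over all three. Give PCA factor scores the same contrast rule as the markers, not Q ≤ 0.3.

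The change needs no new data and no new software. The cost is in power. With n=24, the paired difference detectable with 80% power is 0.60 SD of the difference at an unadjusted 0.05. At 0.0125 per marker, simulation with six balanced sequences (assumed) gives:

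| Rule | Third burger equals one of the pair | Third burger midway |
|---|---|---|
| Overall test first | about 0.75 SD | about 0.79 SD |
| Paired t-tests only | about 0.78 SD | about 0.82 SD |

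For metabolites, adding Q ≤ 0.3 costs essentially nothing if 80-120 differ. If only 20-40 differ, power per metabolite falls from 83-98% to 57-97%.

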3.2 Participants

We will include up to 40 middle aged adults (30-60 years) in this study. Inclusion/exclusion criteria are listed below.

Inclusion criteria:

- Age \ge 30 and \le 60 years;
- BMI \geq 25 and \leq 35 kg/m²;
- Weight stable in last 3 months (Loss or gain <4%);
- Hemoglobin A1C (HbA1C) ≤6.4%;
- Fasting plasma glucose concentration <126 mg/dl;
- For the safety of the participant and proper consent of the procedures, subjects must be able to speak and understand English to participate in this study

Version 1 Page 2 of 9

Exclusion criteria:

- Use of medications that are known to affect the study outcome measures (e.g., NSAIDs, corticosteroids) or increase the risk of study procedures (e.g., anticoagulants) that cannot be temporarily discontinued for this study;
- Consuming >14 drinks per week;
- Use of cigarettes (or other tobacco products) in last 3 months;
- COVID vaccine within the last two weeks;
- Engaged in high-level competitive exercise (e.g., triathlon, marathon, powerlifting);
- Any inflammatory diseases (e.g. autoimmune diseases, coeliac disease glomerulonephritis, hepatitis, inflammatory bowel disease, arthritis);
- Diagnoses of active malignancy, congestive heart failure, diabetes mellitus and/or chronic obstructive pulmonary disease;
- Use of antibiotics in last 60 days;
- Pregnant or planning to in the next month*;
- Lactating women;
- Soy allergy;
- Persons who are unable or unwilling to follow the study protocol or who, for any reason, the research team considers not an appropriate candidate for this study, including non-compliance with screening appointments or study visits.

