4. SUBJECT RECRUITMENT AND COMPENSATION

4.1 Recruitment

Subjects will be recruited by posting flyers in designated areas around USU's campus, through advertisements on social media. In the advertisement, potential subjects for this study will be directed to contact the study team by email or phone to obtain more information about the study, if interested. Participants who are interested will be provided with a copy of the informed consent by email. When the participant expresses interest in being in the study, the study team member will confirm by telephone that the participant meets most of the inclusion/exclusion criteria (ones that can be determined without

Version 1 Page 6 of 9

the need for a blood draw) before scheduling him/her for a consent meeting. Subjects will attend a one-on-one information session that will be conducted by trained member to present the details of the study. We anticipate that we will need to telephone screen, approximately 150 people and that approximately 45 will be consented. We will enroll up to 30 participants to meet our goal of having at least 24 participants complete the study (assuming a 20 % drop-out rate).

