4.2 Compensation

Participants will receive compensation for completing each study procedure for a maximum of \$475, which will be paid at the end of the study. If a participant drops out of the study before completing the entire study, they will be paid according to the degree of completion. Participants will receive \$25 for the screening blood draw visit and \$150 for each of the metabolic visits.

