- o **Power Calculations:** Using untargeted metabolomics for our power calculations of the number of participants we need to recruit, we assume a P-value ≤ 0.05, Q-value ≤ 0.3, and standard deviation of 0.3 based on previous work (Pimentel et al., 2018). Since there are no entirely comparable previous studies available to draw from, the effect size and number of truly different metabolites are meant to give general estimates. 600 metabolites are typically identified (Nieman et al., 2015) and conservative estimation is that 20-40 metabolites will be significantly different with a mean of 0.2624 (30% difference). An n=24 per group is expected to provide true discovery rates ranging from 89-93 % assuming differences in 80-120 metabolites. Assuming a drop-out of 20%, the final number of participants we will recruit is N=30. This, we consider adequate without having to engage more participants than necessary to address the research aims.

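### With 20% drop-out expected, the paired t-tests leave out completed burger visits from people who leave early; a mixed model with burger and period would use them all

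*Combined protocol and SAP*

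**What the plan says.** The design is a randomized cross-over in which each participant eats all three burgers at separate visits (protocol sections 1 and 3.3).

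Section 7, Power Calculations, sizes the study on 24 and allows for losses: "Assuming a drop-out of 20%, the final number of participants we will recruit is N=30". Section 4.1 agrees, stating "our goal of having at least 24 participants complete the study (assuming a 20 % drop-out rate".

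The analysis is one sentence in section 7, Statistical analysis: "Change scores and factor (change) scores for both diets will be compared using paired t-tests". That sentence speaks of two diets although there are three burgers, so the set of contrasts is itself left open. The section defines no analysis population, gives no rule for a missing visit, does not say which visits enter the principal component analysis (PCA), and plans no sensitivity analysis.

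Partial completion is foreseen in two other places. Section 4.2 covers payment: "If a participant drops out of the study before completing the entire study, they will be paid according to the degree of completion". Section 8 lets a person who withdraws after giving samples decide what happens to the unused ones. Neither says how that person's data count.

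**The concern.** A paired t-test needs both members of a pair. Someone who eats one burger and leaves contributes nothing. Someone who eats two contributes to one contrast, or to none if the analysis is limited to completers. The plan does not choose between available pairs and completers only, so the choice could be made after results are seen. With available pairs, the three contrasts also come from partly different people.

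Two things are at stake. The first is precision: test-meal visits are completed and sampled, then left out. The second is possible bias. Early leaving always removes the later visits. If it is related to how a person responded to an earlier burger, or if responses drift from visit to visit, the pairs that remain are no longer a fair sample.

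**Working it through.** **Inputs from the documents.** 24 completers, 20% drop-out and N = 30 (sections 4.1 and 7); three burgers at three visits (sections 1 and 3.3); four blood samples per metabolic visit (section 3.3); SD 0.3 and effect 0.2624 (section 7).

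**Assumed, because the documents are silent.** Correlation between a person's visits (0.3, 0.5 and 0.7 tried), two-sided alpha of 0.05, when people leave, and why.

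**The plan's own figure.** 24 / (1 − 0.20) = 30, which reproduces N = 30. Leavers: 30 × 0.20 = 6. This is an upper limit for partial completers, since some may go before any test meal. (Section 3.2 says "We will include up to 40 middle aged adults (30-60 years) in this study"; 20% of 40 would be 8. The enrolment figures need reconciling.)

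**Precision.** In within-person SD units, a paired contrast on n pairs has SE = √(2/n).

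For all visits in one model, the information on the three burger means is as follows, taking participants as fixed and with I the identity and J the all-ones matrix. A completer gives I − J/3. A person with two visits gives ½vv′, where v is the difference between the two burgers eaten. Summed over the three possible pairs, vv′ equals 3(I − J/3). Two leavers per pair therefore add 2 × ½ × 3 = 3 completer-equivalents: 24 + 3 = 27.

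| All 6 leave after two visits, balanced | Equivalent n | SE | Change in SE |
|---|---|---|---|
| Completers only | 24 | 0.2887 | – |
| Available pairs | 26 | 0.2774 | −3.9% |
| All visits, one model | 27 | 0.2722 | −5.7% |

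For a contrast with 80% power at n = 24 (standardised paired difference 0.597, chosen only to give that power), power is about 83% at 26 and 85% at 27.

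Treating participant as random recovers slightly more. Across correlations 0.3 to 0.7, with period in the model:

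- all 6 leave after two visits: equivalent n 27.2 to 27.5
- 3 leave after one visit and 3 after two: 25.9 to 26.5 (available pairs: 25)
- all 6 leave after one visit: 24.6 to 25.4 (paired tests: 24)

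**Bias from response-related leaving.** Simulation with no true burger difference, equal between- and within-person SD, no drift, and 20% leaving, all after the plant burger. Entries are the error in plant minus beef, in within-person SD.

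| Odds of leaving per 1 SD higher plant response | Completers only | Available pairs | All-visits model |
|---|---|---|---|
| × 2.7 | −0.10 | −0.07 | 0.00 |
| × 7.4 | −0.16 | −0.11 | 0.00 |

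Against the SE, 0.16 / 0.289 = 0.55 and 0.11 / 0.277 = 0.40.

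A more extreme, all-or-nothing link has everyone in the top 30% of plant response leaving if visits remain. At SD 0.3 and correlation 0.5 it gives −0.044 (completers) or −0.031 (available pairs). That is 17% or 12% of the planned 0.2624, and 0.044 / 0.0612 = 0.72 or 0.031 / 0.0588 = 0.53 of an SE. The mixed model with period gives about 0.

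**Bias from drift.** If people leave after the plant burger regardless of response, and there is no drift, no method is biased. With a drift of 0.1 per visit (SD 0.3, correlation 0.5) the error is +0.019 (completers) or +0.024 (available pairs); the mixed model with period gives about 0.

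**The period term is needed.** With the drift set at 0.2 to 0.33 within-person SD per visit, an all-visits model containing burger and participant but not period is off by about +0.04 to +0.07. Adding period brings this to about 0.

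**The case against.** The strongest reply is that the plan protects itself. Enrolment is inflated so that 24 complete, and section 7 sizes the study on 24: "An n=24 per group is expected to provide true discovery rates ranging from 89-93" percent. A completers-only analysis therefore meets its own target, and extra precision is a bonus. That stands for precision, and it is why I call the cost modest. Inflation does not say how leavers' data count, and it does nothing about selective leaving.

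A second reply is that the bias is remote. The paired tests cover inflammatory markers and metabolites measured later from stored samples, and the results shared with participants are clinical laboratory values. A participant cannot see the response in question, so leaving would have to follow it through symptoms. That also stands. The bias figures need leaving to be concentrated after one burger, with a link whose strength I assumed.

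Three stronger readings are tempting, and the documents do not support them.

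- A reader might take section 3.2, which excludes anyone the team "considers not an appropriate candidate for this study, including non-compliance with screening appointments or study visits", as a rule for removing people between test meals. It is an eligibility criterion. Section 3.3 counts the screening and consent visit among the visits, and nothing there speaks of removing enrolled people or discarding data.
- A reader might infer that assay results already in hand would be thrown away. Section 7 stores samples until analysis and does not say that leavers' samples will be assayed.
- A reader might conclude that the contrasts will be biased. Leaving unrelated to response, with no drift, biases nothing.

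**Conclusion.** The point holds as a worthwhile improvement of modest size. The stated analysis certainly leaves out one-visit participants. It uses two-visit participants in at most one of three contrasts, and whether it uses them at all depends on a rule the plan does not give.

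The largest precision loss at N = 30 is 24 against about 27 participants per contrast (SE about 6% smaller with all visits). It requires all 6 to leave after exactly two visits, balanced across burgers. It is smaller if people leave earlier, and for anyone who leaves before a test meal there is nothing to recover.

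Bias is possible but conditional on response-related leaving or on period drift, and the documents quantify neither. Under the strong graded links assumed here it reaches about half a standard error. Only the all-or-nothing link goes further, to about 0.7 for completers only.

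The all-visits model removes this bias only if it includes period and if leaving depends on observed data.

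**What to change.** In section 7, Statistical analysis:

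1. Replace the paired t-tests with one linear mixed model per outcome (PROC MIXED in the SAS already named), with burger and period (visit order) as fixed effects and participant as a random effect.
2. Fit it to all participants with at least one completed metabolic visit, subject to any sample withdrawal under section 8, and take the three burger contrasts from it.
3. Use participant-visits as the PCA rows, so that a missing visit does not remove a person's other visits, and analyse the factor scores with the same model.
4. Report the number leaving by last burger eaten.
5. Give the result in three-visit completers as a sensitivity analysis.

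The cost is wording plus some assays; no participants or visits are added. Leavers' stored samples must be assayed: at most 6 × 2 = 12 visits, or 12 × 4 = 48 plasma samples, plus urine. The model also rests on the assumption that leaving depends only on observed data, which the counts in step 4 and the comparison in step 5 help a reader to judge but cannot prove.

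### The metabolite tests drop the Q ≤ 0.3 criterion that the trial was sized on; at P < 0.05 alone, about 42–63% of flagged metabolites would be false if 20–40 of 600 truly differ (17–28% if 80–120 do).

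*Combined protocol and SAP*

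**What the plan says.** Both texts are in section 7 of the combined protocol and SAP.

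- **Statistical analysis.** Change scores "will be created for all inflammatory biomarkers and metabolites". Metabolite data are also reduced to factors by principal component analysis. Then "Change scores and factor (change) scores for both diets will be compared using paired t-tests", and "P< 0.05 will be considered statistically significant". No Q-value, false-discovery or other multiplicity rule appears.
- **Power Calculations.** The calculation is based on untargeted metabolomics: "we assume a P-value ≤ 0.05, Q-value ≤ 0.3, and standard deviation of 0.3". It takes it that "600 metabolites are typically identified".
- **Number of true differences.** The same paragraph gives two counts. First, "conservative estimation is that 20-40 metabolites will be significantly different with a mean of 0.2624 (30% difference". Then, "An n=24 per group is expected to provide true discovery rates ranging from 89-93 % assuming differences in 80-120 metabolites". It adds that "the effect size and number of truly different metabolites are meant to give general estimates".

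The Q criterion appears only in the power paragraph.

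**The concern.** The number of participants was justified under one decision rule and the results will be judged under another. A threshold of P < 0.05 on each of about 600 metabolites fixes the error rate per test. It sets no limit on the share of flagged metabolites that are false, because that share depends on how many truly differ, and the plan gives two counts that it does not reconcile.

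Metabolites are a stated objective (section 2) and the sole basis for the sample size. Three foods are compared, and a contrast with few real differences is the most exposed. Without a false-discovery rule, a list of apparent diet effects in such a contrast could be mostly noise. Choosing a Q method after seeing the results would itself be a data-driven choice.

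**Working it through.** **Inputs (section 7).** 600 metabolites; mean difference 0.2624 (the log of 1.30); SD 0.3; n = 24; P 0.05; Q 0.3; true differences m = 20–40 or 80–120. Two-sided tests are assumed. The plan does not say whether 0.3 is the SD within each diet or the SD of the paired difference, so both readings are shown.

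**1. The plan's own figures.**
- Recruitment: 24 / (1 − 0.20) = 30, as stated.
- Discovery rate: read it as average power at the P cut-off *t* that solves (600 − m)·t / [(600 − m)·t + m·power(t)] = 0.3, using the normal two-group formula. This gives 87.1% at m = 80 (t = 0.057) and 91.6% at m = 120 (t = 0.098), within 2 points of the stated 89% and 93%.
- A fixed P cut-off gives the same power whatever m is. That the stated rate moves with m indicates that Q was doing work in the sizing.

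**2. Power per truly different metabolite at P < 0.05.** Standardised difference = 0.2624 / 0.3 = 0.875.
- 0.3 as per-diet SD, two-sample t: noncentrality 0.875 × √12 = 3.03, 46 df, power 0.843.
- 0.3 as SD of the paired difference: noncentrality 0.875 × √24 = 4.28, 23 df, power 0.984.

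**3. False share at P < 0.05 alone, one diet contrast.** False = 0.05 × (600 − m); true = power × m; share = false / (false + true).

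| m | False | True (power 0.843 / 0.984) | False share |
|---|---|---|---|
| 20 | 29.0 | 16.9 / 19.7 | 63.2% / 59.6% |
| 40 | 28.0 | 33.7 / 39.4 | 45.4% / 41.6% |
| 80 | 26.0 | 67.4 / 78.7 | 27.8% / 24.8% |
| 120 | 24.0 | 101.1 / 118.1 | 19.2% / 16.9% |

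**4. Where the share reaches 30%.** Setting 0.05(600 − m) = 0.3 × [0.05(600 − m) + power × m] gives m = 21 / (0.3 × power + 0.035), which is 73.0 (power 0.843) or 63.6 (power 0.984). The conservative 20–40 lies below both values, and 80–120 lies above both.

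**5. With P ≤ 0.05 and Benjamini-Hochberg Q ≤ 0.3.** Simulation, 2,000 runs, one contrast of 600 independent metabolites.

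| m | False share (per-diet SD / paired SD) | Sensitivity (per-diet SD / paired SD) |
|---|---|---|
| 20 | 28.7% / 29.3% | 62.3% / 93.5% |
| 40 | 27.8% / 28.2% | 73.3% / 96.7% |
| 80 | 25.9% / 24.4% | 83.1% / 98.4% |
| 120 | 19.0% / 16.8% | 84.2% / 98.4% |

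With correlated metabolites (assumption: blocks of 10, r = 0.5, paired reading, 600 runs) the false shares are 27.8%, 27.5%, 24.2% and 16.4%.

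**6. Pooled or within-contrast Q.** As an illustration, assume 40, 40 and 5 true differences in the three contrasts (1,500 runs). The false share in the sparse contrast is 86–87% at P < 0.05 alone, 69% with Q pooled over contrasts, and 29–30% with Q computed within the contrast.

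**The case against.** - **In the 80–120 scenario the omission changes little.** This stands. P < 0.05 alone already keeps the expected false share below 30%, and adding Q moves it by 2 points at most. But the plan calls 20–40 its conservative estimate and describes such counts as general. Error control should not depend on the favourable count being right.
- **Q ≤ 0.3 is a power assumption, not a reporting limit, and restoring it does not reproduce 89–93%.** Partly stands. The plan never states 30% as a limit for reporting. Requiring P ≤ 0.05 as well as Q ≤ 0.3 gives 83–84% or 98% at 80–120, and the closest two-sided match uses Q alone at cut-offs looser than 0.05. The power paragraph nevertheless names both criteria, and the analysis text applies only one.
- **The component analysis may take care of multiplicity.** One could read the text as testing biomarkers by change score and metabolites only by factor score. Taken literally, it creates change scores for every metabolite and tests change scores as well as factor scores, and the power paragraph counts individual metabolites. The literal reading is the stronger one.
- **The number of tests is not fixed.** This stands. Targeted assays are also allowed, so 600 is the plan's typical figure only.
- **Q controls an average.** This stands. With 20 true differences (per-diet or paired SD not separated in that check), the realised false share under the proposed rule ranged from about 8% to 48% (5th to 95th percentile).

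**Conclusion.** The concern holds and should be settled before analysis. The metabolite tests lack the Q criterion used to size the trial. At P < 0.05 alone, the expected false share per contrast is about 42–63% if 20–40 metabolites truly differ and 17–28% if 80–120 do. The practical harm lies in the first scenario and in any contrast with fewer than about 64–73 true differences.

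These figures are expectations for one contrast. They assume exactly 600 metabolites, a common effect of 0.2624, n = 24 completers and two-sided tests; each range spans the two readings of the SD. That the rule is missing depends on none of these assumptions.

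**What to change.** **Statistical analysis.** For metabolite-level tests, replace the P-only criterion with: P ≤ 0.05 and Benjamini-Hochberg Q ≤ 0.3, with Q computed over all metabolites within each diet contrast, and within each sample type and time point tested. Keep P < 0.05 alone only for the non-omics tests. The plan names neither the Q method nor the family, so both must be written down. Within-contrast Q is proposed because pooling protects only the overall share.

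**Power Calculations.** State which count, 20–40 or 80–120, the sample size rests on.

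**Cost.** Two short text changes and no new data or participants. Fewer metabolites will be flagged:
- 20–40 differ: sensitivity falls from 84% to about 62–73% (0.3 as per-diet SD), or from 98% to about 93–97% (0.3 as SD of the paired difference).
- 80–120 differ: the loss is about 1 point at most (largest at 80 under the per-diet reading, 84.3% to 83.1%).
- 5 of 600 differ: sensitivity falls to about 41% or 81% under the two readings.
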